#### *Determine the efficacy to achieve successful PVC suppression and rate of adverse events between RFA and AAD treatment arms.*

The best PVC suppression strategy (RFA vs. AADs) in subjects with PVC-CM is not known due to the lack of head-to-head comparison. Moreover, The rate of responders, successful PVC suppression (defined as 80% PVC reduction), adverse events and treatment crossover between these 2 treatment arms is unknown. We plan to assess and compare clinical benefits (QOL, NYHA class, HF symptoms, morbidity and mortality, avoidance of device implants) and secondary end-points (composite adverse events,

composite arrhythmia burden and efficacy of PVC suppression) between RFA and AADs in a large randomized PAPS study.

After treatment randomization in the proposed PAPS pilot study, all data will be compared between RFA and AAD throughout the 12-month follow up to determine the change in PVC burden, clinical outcomes including adverse events and treatment crossover between both distinct treatments. We hypothesize that RFA is better than AADs to improve LV function, HF symptoms, while decreasing heart failure admissions, arrhythmia burden, heart failure admissions, and avoid the need for a defibrillator.

*This pilot study will allow us to determine the rate of successful PVC suppression (greater than 80% PVC reduction), adverse events and 6-month treatment crossover between both RFA and AADs, which in turn will allow us to properly design and power the large randomized PAPS study.*

### **G. Data collection**

Using a subject questionnaire and through medical records, we will obtain and record baseline demographics, including age, gender, race, ethnicity, duration of cardiomyopathy and prior LVEF, history of atrial fibrillation, and medical therapy including dosing prescription. All procedures and tests to be performed during the observation and treatment period (RFA vs. AADs group) are outlined in Figure 1 and Table 2.

*Data will be collected and recorded* directly by the research coordinator and local investigator and as per protocol. A unique identifier will be given to each subject. All participating institutions will be required to complete and submit all data directly to the Coordinating Center via a secure encrypted data capture system (REDCap). In addition, we will request all centers to scan a copy of all completed questionnaires and forms through REDCap. All participating sites will comply with all applicable laws, regulations and provisions related to the subject's privacy and data confidentiality (see details in Protection of Human Subjects).

*Data quality and consistency of intervention* (RFA of PVCs) will be facilitated and monitored by 1) standardized subject's research study forms to be completed by all centers, 2) review of subject's data/forms as study visits are completed, 3) complications/adverse events, and 3) effectiveness of PVC suppression by Data Safety Monitoring Board (DSMB) and during PAPS investigators annual meeting. In contrast, the quality of echocardiogram, Zio Patch Holter monitors and CMR will be monitored by Echo, Holter and CMR core laboratories, respectively.

### **H. Limitations**

The following limitations may arise during the development of this project:

1. Subjects with progression from mild and moderate to severely symptomatic PVCs (incapacitating palpitations and dizziness) will be encouraged to complete the 3-month observation period since PVC suppression will initiate immediately thereafter. Subjects are excluded if symptoms preclude completion of the 3-month observation.
2. Limited or poor suppression of PVC suppression in randomized treatment (RFA or AAD) arm. These subjects are encouraged to remain on the assigned arm. However, crossover to the alternate treatment arm can be considered after 6 months only if considered medically indicated. If crossover were to occur before 6 months, immediate notification and final evaluation with echocardiogram and ambulatory ECG Holter monitor (Zio Patch) should be obtained prior to crossover, and the subject will be excluded from study and followed in a PVC-CM registry if consent was provided (described above Section A.1).
3. PVC variability or spontaneous resolution of PVCs may limit pre vs post procedure comparison. PVC burden has significant temporal variability and it may be a major limitation in the study of arrhythmias. Schmidt demonstrated that an 80% absolute reduction of PVC burden is required to show a true drug effect. To minimize daily PVC variability, PVC evaluation in this study will be performed using a 2-week ambulatory ECG Holter monitor (Zio Patch, IRhythm, Inc.) which is shown to be a better indicator of long-term PVC burden.
4. LV function assessment in ventricular bigeminy. Assessment of LVEF during frequent PVCs represents a challenge for all imaging modalities. Modified acquisition and post-processing methods have been developed to correct for R-R interval variability expected with frequent PVCs. In the event that the subject has persistent ventricular bigeminy at the time of the scheduled echocardiography, the LV function assessment should be postponed for a few hours or a later date when PVCs are less prominent (at least ventricular quadrigeminy).

5. Non-indicated clinical visits, ECGs and cardiac imaging. Due to limited funds provided by R34, the protocol relies mostly on clinically indicated follow up visits and cardiac imaging for subjects with HF and frequent PVCs undergoing PVC suppression strategy. Table 2 and Figure 1 detail the visits and procedures recommended for this study. However, some visits, testing and imaging may be considered outside of standard of care (noted on asterisk). It is left to the local PI to attempt to obtain/request these tests if considered clinically indicated. *This pilot study will also help us determine the number of visits, tests and imaging (echocardiograms and cardiac MR) that is clinically indicated to better plan a budget for the large-scale PAPS study.*

6. ICD implantation for primary prevention is not encouraged during the study as the CM may improve or even resolve after RFA of PVCs as recently shown by Penela et.al. If an ICD is present or the practitioner decides to implant an ICD prior to completion of the study; programming to VVI 40 or other pacing algorithm should be considered to ensure minimal ventricular pacing.

### **I. Statistical analysis and sample size estimate**

All results will be reported according to the CONSORT guidelines. Specifically, all study data will be summarized by means and standard deviations or frequencies and percentages. Fisher's exact tests and Wilcoxon rank-sum tests will be used to compare demographic and baseline injury severity information between the treatment regimens to ensure proper randomization. The unadjusted relative risk between each potential predictors at each time point will be calculated. An extended model will consider the change in the relative risk values over time while also assessing if the relationship between outcome and predictor depended on the baseline PVC burden. Similar analyses will be performed for each of the secondary outcomes. Lastly, the adverse events will be summarized separately for each treatment group using frequencies and percentages. Similar summaries will be provided for each of the PVC burden levels. The software SAS/STAT® Software (SAS Institute, Inc. Cary, NC) will be used for all statistical analysis.

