**Table 2. Table of Study Procedures**

	3-month Observation			12-month Treatment Phase					
	Obs-V1 Baseline	Obs-V2 2-mo	Obs-V3 3-mo	Tx-V1 Baseline	Tx-V2 1-mo	Tx-V3 3-mo	Tx-V4 6mo	Tx-V5 9-mo*	Tx-V6 12-mo
Timeline in Weeks (range of days)	Week 0 (Day 0)	Week 9 (51-63)	Week 12 (84-96)	Week 12-15 (84-105)	Week 21 (141-153)	Week 26 (176-188)	Week 38 (260-272)	Week 50 (344-356)	Week 64 (441-454)
Informed consent	X								
Inclusion/Exclusion Criteria	X								
Collection of demographic data	X								
Medical History	X								
Physical Exam	X		X		X	X	X	X	X
Functional status/NYHA class	X		X		X	X	X	X	X
QOL Minnesota HF Questionnaire	X		X		X	X	X	X	X
Current / change of medications	X		X		X	X	X	X	X
12-lead ECG	X*	X*	X		X*	X*	X*	X*	X*
Ziopatch	X	X ‡			X €	X	X		X
Echo	X £		X ‡			X	X*		X
BNP / ProBNP levels ESR & CRP	X* £		X*		X*	X*	X*	X*	X*
Urine pregnancy test (if applicable)	X		X	X	X	X	X	X	X
CMR	X*								
TSH (if assigned to amiodarone)			X				X		X
LFT (AST) (if assigned to amiodarone)			X				X		X
Treatment randomization	X								
Initiation of RFA or ADD				X					

Collection of unsolicited AEs	From Obs-Visit 1 until Tx-Visit 6
--------------------------------------	-----------------------------------

Footnote: \*, visit/intervention if clinically indicated.

‡ LVEF results of 2D-echocardiogram and Ziopatch have to be available at the time of Observation Visit 3 (Obs-V3). € If PVC burden >10%, subject should be considered to either adjust antiarrhythmic therapy (AAD group) or second ablation procedure (RFA group) based on their randomization group. ESR, Erythrocyte sedimentation rate; CRP, C-reactive protein. £ Must be done within 150 days of Enrollment Visit (Day 0)

Crossover between PVC suppression strategies is not encouraged. We request that crossover only be considered after 6 months of initiation of treatment, for which an intention-to-treat analysis will be performed. However, if crossover occurs before 6 months of initiation of treatment, subjects will be withdrawn from the study and included in the PVC-CM registry if the subject provided consent.

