#### **E. Primary and secondary outcome measures.**

*The outcomes are divided in primary and secondary end-points (Table 3).*

*The primary end-points will consist of:*

1. *Improvement of LVEF after PVC suppression at 12-month follow-up.* This is chosen as primary-end point due to the known prognostic value of LVEF. The lower the LVEF, the higher the risk of sudden cardiac death and heart failure. This will compare the overall improvement or change in LVEF between RFA and AAD groups. This end-point will support that either RFA or AADs have an overall better outcome due to significant improvement of LV function with potential impact on morbidity and mortality associated with PVC-CM.

2. *Responders to PVC suppression strategy at 12-month follow-up* (See rationale under Section “Definitions” in 3rd paragraph of Aim 2). Assessment of the number of responders (delta LVEF  $\geq$  10%) after PVC suppression strategies (RFA or AADs) will assess the effectiveness of RFA and AADs to reverse or improve cardiomyopathy induced by frequent PVCs. Evidence that either RFA or AADs is superior to improve or even reverse LV dysfunction in subjects with high burden PVCs could have significant impact of morbidity and mortality including future heart failure and ventricular arrhythmias, and also may avoid ICD implantation.

*The secondary end-points will consist of:*

1. *Efficacy of RFA vs AADs groups to achieve successful PVC suppression at 12-month follow-up, defined as a reduction of PVC burden  $\geq$ 80% (regardless of LVEF change). Understanding the success rate of PVC suppression between RFA and AADs will help better determine the best treatment to those subjects with high PVC burden.*

2. *Composite end-point of adverse events at 12-month follow-up, including worsening in NYHA functional class (I-IV), number of HF and cardiac-related admissions, RFA complications and AAD adverse effects and cardiovascular death.*

This adverse event composite end-point is chosen to understand the overall complications and adverse effects/events related to RFA and AADs. Worsening of NYHA functional class will be defined as when/if the subject’s functional status worsens by one NYHA class. Hospital admissions will be defined as any visit to ED or hospital admissions related only to a cardiovascular event such as heart failure, angina, pre/syncope and palpitations.

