#### Sample size justification.

*This has been estimated solely on primary end-point of improvement in LV ejection fraction after PVC suppression. We are planning to compare the improvement in LVEF between PVC suppression strategies (RFA vs. AADs groups). Due to the multiple random effects, a simulation study was conducted to estimate the number of subjects required for this study. Specifically, data was simulated according to a linear mixed-effects model with an unstructured error structure with a random site effect. It was assumed that subjects would have a LVEF level of 25% (SD=5%) in each of the groups at baseline and LVEF levels of 40% and 35% (SD=10%) in the RFA and AAD groups at 12 months, respectively. A within subject correlation of 0.25 was assumed along with an inter-site standard-deviation of 1%. *This model was fit assuming that, on average, 10% of the subjects would drop out randomly.* Approximately 140 total subjects (70 per group) should be enrolled to reject the null hypothesis that the mean LVEF between RFA and AAD groups are equal with probability (power) 0.8 and Type I error probability of 0.05. *As a pilot study we have determined the need to enroll at least 20% (30 subjects) of preliminary sample size estimation to understand feasibility and key aspects of subject enrollment, randomization and retention to properly power a large-scale randomized PAPS study. Sample size is increased by 15% (6-9 additional subjects, 36-39 subjects total – between 19-20 subjects in each treatment group) to take into account possible spontaneous improvement of LV dysfunction during the 3-month observation period between treatment strategies.**

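### Section I names only a relative risk as an outcome statistic, which does not fit the LVEF-change primary endpoint, and baseline LVEF is not tied to one visit

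*Combined protocol and SAP*

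**What the plan says.** Section E makes change in LVEF at 12 months the first primary endpoint: "This will compare the overall improvement or change in LVEF between RFA and AAD groups". Responder status, a gain of at least 10 points, is the second.

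The analysis text of Section I has these elements:
- Description: "all study data will be summarized by means and standard deviations or frequencies and percentages".
- Fisher and Wilcoxon tests, for baseline comparability only.
- An outcome statistic: "The unadjusted relative risk between each potential predictors at each time point will be calculated".
- An extension that follows the relative risk over time while "assessing if the relationship between outcome and predictor depended on the baseline PVC burden".

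The sample size justification, under the same Section I heading, says more: "We are planning to compare the improvement in LVEF between PVC suppression strategies (RFA vs. AADs groups". There, "data was simulated according to a linear mixed-effects model with an unstructured error structure with a random site effect", and the stated aim is to "reject the null hypothesis that the mean LVEF between RFA and AAD groups are equal".

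In Section F (rate of responders), the change is final minus baseline LVEF, with no visit named. Table 2 labels the Week 0 column "Obs-V1 Baseline" and gives the Week 12-15 treatment column the same label. The Definitions call Week 0 the baseline visit; Section B calls Treatment Visit 1 the baseline visit. Section E ties baseline to the pre-treatment value, but only for PVC burden. Echoes are scheduled at Week 0 (qualifying echo up to 150 days old) and Week 12.

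**The concern.** A relative risk suits the responder endpoint. It cannot express a difference in mean LVEF change, so the analysis text gives the first primary endpoint no estimator, interval, covariates or time point. The stratum that the plan considers necessary at randomisation enters only as a possible effect modifier.

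The stake is estimation. The pilot exists to design and power the full trial, and the Data Sharing Plan says it is not meant to settle which strategy is better. The full trial is sized on a mean difference, an SD and a within-subject correlation, and those are what the pilot should report.

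The undefined baseline is a separate problem. Two analysts could take different echoes and obtain different responder counts from the same data. In an open-label trial that choice should be fixed before outcomes are seen.

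**Working it through.** **Inputs (sample size justification, Section I).** Baseline LVEF 25% (SD 5); 12-month LVEF 40% versus 35% (SD 10); correlation 0.25; dropout 10%; alpha 0.05 (taken as two-sided); power 0.80; 140 in total. Pilot: 30 subjects before the allowance, 36-39 after it.

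**1. Reproducing the plan's figure.** SD of change = √(5² + 10² − 2×0.25×5×10) = 10.0. Per arm, n = 2×(1.960 + 0.842)²×10²/5² = 62.8, so 63. Then 63/0.9 = 70 per arm, 140 in total. This matches. A one-sided test would give 112. The trial is therefore sized on a difference in means.

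**2. Power at 63 evaluable per arm.**
- Unadjusted mean difference (SD 10.0, noncentral t): 0.795.
- Baseline-adjusted (SD = 10×√(1 − 0.25²) = 9.68): 0.820.
- Responder relative risk, assuming normal changes with SD 10: RFA Φ((15 − 10)/10) = 0.691, AAD Φ((10 − 10)/10) = 0.500, RR = 1.38. Power of the Wald test on log RR, by exact enumeration: 0.576.

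**3. Pilot precision.** The evaluable number is an assumption, so a range is shown. Half-width = t(0.975, 2n − 2)×10×√(2/n).

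| Evaluable per arm | LVEF difference, half-width | RR 1.38, 95% CI |
|---|---|---|
| 15 (30/2) | 7.5 | 0.75 to 2.54 |
| 16.2 (36×0.9/2) | 7.2 | 0.77 to 2.48 |
| 17.55 (39×0.9/2) | 6.9 | 0.79 to 2.43 |

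The adjusted formula suggests a gain of about 0.2 point. When the model with arm, Week-0 LVEF and stratum is fitted to simulated data, the gain is smaller: 7.40 versus 7.34 (30 subjects, no dropout), 7.15 versus 7.08 (36, 10% dropout), 6.87 versus 6.79 (39, 10% dropout). A separate simulation at 16 per arm gave 7.14 unadjusted and 7.18 adjusted. The change is 0.1 point or less and can go either way.

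The other planning inputs would also be loose: an SD of 10 on 28 degrees of freedom has a 95% CI of 7.9 to 13.5, and a correlation of 0.25 from 30 subjects has −0.12 to 0.56.

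**4. Which baseline echo.** Suppose LVEF drifts up 5 points in both arms during observation (illustrative), with the SD of change held at 10.
- If the planned 15- and 10-point gains run from Week 12, counting from Week 0 makes them 20 and 15. Responders: Φ(1.0) = 0.841 and Φ(0.5) = 0.691. RR moves from 1.38 to 1.22.
- If the gains run from Week 0, counting from Week 12 makes them 10 and 5. Responders: Φ(0) = 0.500 and Φ(−0.5) = 0.309. RR moves from 1.38 to 1.62.

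The expected mean difference is 5 in every case.

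**5. Is 5 points plausible?** The plan expects under 15% responders during observation. The SD of the observation-period change is not given. With SD 5 at both visits and correlation 0.25 (assumed) it is √(25 + 25 − 12.5) = 6.1, and 5 points of drift implies Φ((5 − 10)/6.1) = 21% responders. At SD 10 it implies 31%. A 15% ceiling allows at most 10 − 1.036×6.12 ≈ 3.7 points at SD 6.1, and no upward drift at SD 10. At 3.7 points, step 4 gives RR 0.808/0.644 = 1.25 or 0.552/0.356 = 1.55.

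**The case against.** The strongest reply is that Section I, read whole, does describe a mean comparison. The sample size justification states the intent, gives a null of equal means, and says the mixed model was fitted. This stands in part. A reader might infer that the plan never intends to compare mean LVEF; the documents do not support that. What is missing is the step from the sizing model to a declared analysis.

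Second, the relative-risk sentence speaks of potential predictors and never names the arms. It may describe predictors of response, so it should not be read as an explicit RFA versus AAD analysis. It is the arm comparison only in that no other outcome statistic is named.

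Third, a reader might infer that the planning inputs would be lost. They would not. Means, SDs and counts by arm yield the unadjusted difference and its interval. The SDs at both visits and of the change yield the correlation: (s₁² + s₂² − s_Δ²)/(2s₁s₂), which on the plan's figures is (25 + 100 − 100)/(2×5×10) = 0.25.

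Fourth, it is tempting to say that the baseline choice swings the relative risk from 1.22 to 1.62. Those ends belong to two alternative assumptions and cannot both apply.

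Fifth, the power of 0.58 concerns the future trial, and the pilot's main aim is feasibility. That is correct. It shows only that a relative risk cannot stand in for the analysis that was sized.

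**Conclusion.** The concern holds as a gap in declaration and a mismatch of statistic to endpoint; it should be corrected but does not threaten the pilot's feasibility aim. The relative risk fits the responder endpoint only, and the mean comparison used for sizing is not carried into the analysis text. On the plan's assumptions the two analyses differ materially at full size (power 0.80, or 0.82 adjusted, against 0.58). At pilot size the LVEF difference will be known to about ±7 points against a planned 5, so it is an estimate and not a test. Adjustment matters for matching the analysis to the design, and hardly at all for pilot precision.

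The baseline ambiguity is real. It affects responder rates and the relative risk, but not the expected mean difference if drift is equal in both arms. The 5-point illustration is hard to square with the plan's own hypothesis, so smaller shifts are more likely. The documents do not show that either echo is the only correct baseline. The figures rest on normal changes, an SD of change of 10 from either echo, and the evaluable numbers shown.

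**What to change.** **Section I, primary endpoint 1.** Analyse 12-month core-lab LVEF with a linear model, or the mixed model already used for sizing, containing arm, the 20% PVC-burden stratum and Week-0 (pre-randomisation) LVEF. Report the adjusted RFA minus AAD difference with its 95% CI, plus the SD and the baseline-to-12-month correlation, as planning estimates and not tests.

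**Section I, primary endpoint 2.** Keep the relative risk, account for the stratum, and add the risk difference.

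**Analysis set.** Keep the intention-to-treat set that the plan declares. Report Week-12 withdrawals and crossovers before 6 months by arm.

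**Section F.** Name one baseline echo for both LVEF change and responder status, and report the other as a sensitivity analysis. Which is primary is the sponsor's choice: Week 0 precedes open-label allocation but includes any gain during observation, while Week 12 isolates change after suppression. Also correct the phrase that places the end of observation before randomisation; the Definitions randomise at Week 0. That phrase belongs to the pooled own-control comparison at 3 months, not to the 12-month arm comparison.

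**Cost.** A few sentences, a few lines of SAS and two degrees of freedom, with no new visits or tests. The Week-0 echo may be up to 150 days old, so the precision gain may be small.

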**A. Study Population and Eligibility**

This is a prospective randomized pilot study including between 36-39 subjects with cardiomyopathy (CM) and high PVC burden with a likely diagnosis of PVC-CM, where all subjects will be assigned to a 1:1 random allocation to one of two un-blinded PVC suppression groups: 1) PVC radiofrequency ablation (RFA) vs. 2) antiarrhythmic drugs (AADs).

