**Definitions:**

The *diagnosis criteria for PVC-CM* is based on LVEF  $\leq$  45% (by echocardiography) and average PVC burden  $\geq$  10% in an ambulatory ECG Holter monitor that meet the inclusion and exclusion criteria (Table 1), regardless of severity and time of onset. LVEF and PVC burden must be within 150 days of Enrollment Visit (Day 0).

*Responders are defined as an LVEF increase greater than 10% points regardless of intervention.*

If screening confirms eligibility (LVEF  $\leq$ 45% and PVC burden  $\geq$  10%), a baseline visit will be scheduled to obtain subject's demographics and medical history, 12-lead ECG, Minnesota living with HF quality of life (QOL) questionnaire, NYHA functional class and cardiac magnetic resonance (CMR) if clinically indicated. Subjects that refuse enrollment, will be asked to participate in a PVC-CM registry to follow their response and crossover to different treatment strategies.

If subjects meet inclusion criteria (Table 1) during screening, informed consent should be obtained. Stratified randomization to either RFA or AADs will be performed at the time of enrollment (baseline visit, week 0). Based on our preliminary data, we expect that around 30% of subjects will have a PVC burden  $>$ 20%. Thus, a *stratified randomization based PVC burden (assessed by Holter) above and below 20% is needed to assure that subjects in both groups (RFA vs. AAD) are equally distributed between PVC burden above and below 20%.* Stratified randomization will be performed using approved software available at the Coordinating Center only.

If a subject is randomized to the RFA arm, a RFA procedure (Visit 1) should be scheduled at the time of randomization due to usual 8-week next available RFA appointment in most participating centers. Yet both, RFA and AAD interventions should only occur or be initiated after completion of a 3-month observation (Table 2 - Visit Tx-V1, week 12-15).

A 3-month observation period will assess spontaneous variation of PVC burden and improvement or deterioration of LV function. During the final 3-month observation visit (Week 12), LVEF and Holter will be repeated to confirm eligibility if PVC burden and LVEF remains  $\geq$ 10% and  $\leq$ 45%, respectively.

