A few small studies suggest that an overall PVC burden more than 20% may affect LV function and NYHA functional class. In contrast, PVC burden of less than 10% is less likely associated with impairment of LV function. Interestingly, a few studies with PVC burden as low as 10 PVCs per hour have shown some degree of improvement in LV ejection fraction after PVC suppression. Based on limited data, we chose  $\geq 10\%$  PVC burden as inclusion criteria for our study, as we believe these are subjects with a higher likelihood of a diagnosis of PVC-CM.

As proposed in this study, we have an observation period that would allow us to assess and compare no active intervention (3-month observation) vs. PVC suppression (treatment phase). Moreover, our study design will allow us to compare two PVC suppression strategies: 1) RFA versus 2) AADs. Successful PVC suppression is defined as a decrease in 80% of PVC burden after 2-4 weeks of procedure. Single RFA of PVCs has been shown to be successful in more than 80% of cases. As in current practice, we plan to repeat a second RFA after 4-6 weeks on those subjects with unsuccessful RFA (less than 80% decrease in PVC burden after RFA group). Since all subjects will start or continue optimal medical therapy regardless of treatment randomization, they will be followed approximately every 3 months in order to assure compliance and assess potential side effects.

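### Randomisation is stratified by PVC burden at 20%, but the plan never commits to including that stratum in the RFA-versus-AAD comparison

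*Combined protocol and SAP*

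**What the plan says.** The design part is clear. Section A of Part I states that "all subjects will be assigned to a 1:1 random allocation", and its Definitions say that "stratified randomization based PVC burden (assessed by Holter) above and below 20% is needed", because "we expect that around 30% of subjects will have a PVC burden" over 20%. The paragraph on avoidance of bias and the Protection of Human Subjects section repeat this. The latter gives a prognostic reason: "A few small studies suggest that an overall PVC burden more than 20% may affect LV function and NYHA functional class".

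The analysis part, section I, is less clear. Its core sentence is "The unadjusted relative risk between each potential predictors at each time point will be calculated". An extended model then looks at change in the relative risks over time, while also "assessing if the relationship between outcome and predictor depended on the baseline PVC burden". The same approach is promised for the secondary outcomes, and after the sentence on adverse events the plan adds "Similar summaries will be provided for each of the PVC burden levels". The section names no between-arm model or test for change in LVEF, the first primary endpoint.

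The only LVEF model in the documents is the one simulated under the sample size justification: a linear mixed model with a random site effect. No term for the PVC stratum is mentioned.

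**The concern.** A factor important enough to stratify on should normally appear in the analysis. Balancing the arms within strata reduces the true sampling variance of the arm difference by the share of outcome variance that the stratum explains. A model without the stratum does not credit that reduction: it returns the variance of an unstratified trial. If the stratum predicts outcome, the confidence interval is too wide and the test rejects less often than its nominal level.

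A second consequence matters more for a pilot. The residual SD estimated here is meant to help power the full trial. An SD from an unstratified model includes between-stratum variation that a stratum-adjusted full trial would remove.

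The effect-modification analysis does not close the gap. It asks whether an association differs by PVC burden and does not commit to a stratum-adjusted arm effect. It also does not say whether burden enters as the 20% stratum or as a continuous value.

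**Working it through.** **Inputs from the documents.** 1:1 allocation; about 30% above 20% burden; 12-month LVEF 40% v 35%, SD 10; baseline SD 5; within-subject correlation 0.25; power 0.80; type I error 0.05 (taken as two-sided); 10% dropout; 70 per group in the full trial; 19 to 20 per group in the pilot.

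**Assumed.** d, the LVEF difference between the high and low PVC strata. The documents give no value, so a range is shown. The arms are taken as balanced within each stratum.

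**Step 1: the plan's own figure.** n per arm = 2 × (1.960 + 0.842)² × 10² / 5² = 62.8, so 63. Dividing by 0.90 gives 70 per arm, 140 in total, which matches the plan. The change score gives the same answer, since its SD is √(25 + 100 − 2 × 0.25 × 5 × 10) = 10. The 140 therefore reproduces with no stratum term.

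**Step 2: LVEF, effect of omitting the stratum.** With total SD held at 10, the stratum explains R² = 0.3 × 0.7 × (d/10)². The correct standard error is √(1 − R²) times the unadjusted one. The unadjusted 5% test has actual size 2 × [1 − Φ(1.96/√(1 − R²))]. Each case was also checked with 20,000 simulated stratified trials.

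| d (points) | R² | Unadjusted SE ÷ correct SE | Size, formula | Size, simulated (63 / 19 per arm) | Power at 63 per arm, simulated, unadjusted → adjusted | Power at 19 per arm, simulated, unadjusted → adjusted |
|---|---|---|---|---|---|---|
| 0 | 0 | 1.000 | 0.050 | 0.049 / 0.052 | 0.791 → 0.791 | 0.321 → 0.320 |
| 5 | 0.0525 | 1.027 | 0.044 | 0.044 / 0.044 | 0.805 → 0.821 | 0.313 → 0.335 |
| 10 | 0.210 | 1.125 | 0.027 | 0.027 / 0.026 | 0.821 → 0.878 | 0.297 → 0.394 |

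At d = 10 the simulated ratios are 1.782/1.585 = 1.12 (63 per arm) and 3.251/2.878 = 1.13 (19 per arm). At d = 2 the standard error changes by only 0.4%. In every scenario the empirical spread of the estimate is the same with and without adjustment. The design has already delivered the precision; the unadjusted model fails to report it.

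**Step 3: what is carried to the full trial.** Residual SD = 10√(1 − R²), which is 10.0, 9.7 and 8.9 at d = 0, 5 and 10. With the Step 1 formula the full-trial total becomes 140, 134 and 112.

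**Step 4: relative risks at pilot size.** Let the responder rate in the high stratum be k times that in the low stratum (assumed). For an arm with overall rate p, the low-stratum rate is l = p/(0.7 + 0.3k) and the high-stratum rate is h = kl. The variance of log p̂ is (1 − p)/(np) ignoring strata, and [0.7·l(1 − l) + 0.3·h(1 − h)]/(np²) respecting them; the two arms are summed. Example with n = 19, rates 0.69 v 0.50 (implied by mean changes of 15 and 10 with SD 10) and k = 1.4: SE 0.276 against 0.271, or 1.9% smaller. Over that pair and 0.50 v 0.28, 0.65 v 0.28 and 0.35 v 0.35, the reduction is 0.3% to 0.8% at k = 1.25 and 0.7% to 1.9% at k = 1.4. A simulation of 40,000 trials with 35% responders and k = 2.0 gave a Mantel-Haenszel standard error 3.6% smaller, with test size 0.030 adjusted and 0.022 unadjusted.

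**The case against.** A reader might infer that the plan declares its main RFA-versus-AAD comparison unadjusted, and that size 0.027 and lost power describe that analysis. The documents do not support this. The sentence with the word unadjusted concerns potential predictors and relative risks, and arm is not named. The larger figures above are for continuous LVEF, whose between-arm analysis is not specified either way. One can argue that the relative-risk analysis must be the primary-outcome analysis, since the secondary outcomes are to follow the same pattern and no other outcome comparison is described. That is reasonable, but it remains an inference.

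Other objections also stand in part:

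- The prognostic rationale is hedged and concerns impairment, not recovery at 12 months. A difference of 10 points is a full outcome SD and twice the assumed treatment effect. The stratum may come from a single Holter of at least 24 hours, while the Limitations section stresses how much PVC burden varies over time, which would weaken its prognostic value.
- The direction is benign: no excess false positives, no bias, and an unadjusted SD would size the full trial cautiously.
- Section I does not ignore PVC burden. A conventional interaction model would include its main effect, though the text does not say so.
- For binary endpoints at this size, small numbers cause most of the conservatism, and adjustment does not restore nominal size.
- The pilot's aim is feasibility, and its data-sharing text says the data are not meant to settle treatment benefit.

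None of this supplies the missing commitment to use the stratum in the arm comparison.

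**Conclusion.** The point holds as a gap in specification with a cheap improvement. The stratum is used to randomise and is not committed to the arm comparison, and for LVEF change no between-arm model is named at all.

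The cost depends on a stratum effect that the documents do not give. For LVEF it runs from nothing at d = 0, through about 3% of the standard error at 5 points, to 12% to 13% at 10 points (equivalently, adjusting makes it 11% smaller). For relative risks at 19 per arm it is about 0.3% to 4%. Pilot power is low with or without adjustment, at 0.30 to 0.39 in the simulations. The practical consequence is therefore modest and lies mainly in the residual SD used to plan the full trial. It would be wrong to infer a false-positive risk, or an error in the planned 140: that figure reproduces exactly and is on the cautious side if the stratum proves prognostic.

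**What to change.** In section I, replace the loose relative-risk sentence by named between-arm analyses:

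- **LVEF change:** a linear model with treatment arm and the randomisation stratum (PVC burden above 20% v 20% or below, coded as entered at randomisation) as a covariate. Report the residual SD from this model for planning the full trial.
- **Responders and other binary endpoints:** a stratum-adjusted relative risk, by Mantel-Haenszel or by Poisson regression with robust variance.
- Show the unadjusted figure beside each adjusted one.
- Keep the PVC-burden interaction as a separate, exploratory analysis, and say whether it uses the stratum or continuous burden.

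The cost is a few sentences in the plan, one covariate that is already recorded, and one degree of freedom. At d = 0 the simulations show no measurable penalty (power 0.791 both ways at 63 per arm, 0.321 v 0.320 at 19). The 140 in the sample size justification needs no change.
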